## APPENDIX 1: Hybrid SLEDAI with SSFI and PGA

(Circle in SLEDAI Score column if descriptor is present at the time of the visit or in the preceding 4 weeks) (The same instrument can also be used going back only ten days)

Item no.	SLEDAI SCORE	Descriptor	Definition
1	8	Seizure	Recent onset, exclude metabolic, infectious or drug causes
2	8	Psychosis	Altered ability to function in normal activity due to severe disturbance in the perception of reality. Include hallucinations, incoherence, marked loose associations, impoverished thought content, marked illogical thinking, bizarre, disorganized, or catatonic behaviour. Exclude uraemia and drug causes
3	8	Organic brain syndrome	Altered mental function with impaired orientation, memory, or other intellectual function, with rapid onset and fluctuating clinical features, inability to sustain attention to environment, plus at least 2 of the following: perceptual disturbance, incoherent speech, insomnia or daytime drowsiness, or increased or decreased psychomotor activity. Exclude metabolic, infectious or drug causes
4	8	Visual disturbance	Retinal changes of SLE. Include cytoid bodies, retinal hemorrhages, serous exudates or hemorrhages in the choroid, or optic neuritis, scleritis or episcleritis. Exclude hypertension, infection, or drug causes
5	8	Cranial nerve disorder	New onset of sensory or motor neuropathy involving cranial nerves
6	8	Lupus headache	Severe, persistent headache; may be migrainous, but must be non-responsive to narcotic analgesia THIS WOULD RARELY BE ATTRIBUTED TO SLE...ALMOST NEVER SCORED
7	8	CVA	New onset Cerebrovascular accident(s). Exclude arteriosclerosis
8	8	Vasculitis	Ulceration, gangrene, tender finger nodules, periungual infarction, splinter hemorrhages or biopsy or angiogram proof of vasculitis
9	4	Arthritis	> 2 joints with pain and signs of inflammation (i.e. tenderness with swelling or effusion)
10	4	Myositis	Proximal muscle aching/weakness, associated with elevated creatinine phosphokinase (CK)/aldolase, or EMG changes or a biopsy showing myositis
11	4	Urinary casts	Heme-granular or RBC casts
12	4	Hematuria	> 5 RBC/high power field. Exclude stone, infection or other cause
13	4	Proteinuria	> 0.5 gram/24 hours
14	4	Pyuria	> 5 WBC/high power field. Exclude infection
15	2	Rash	Inflammatory type rash
16	2	Alopecia	Abnormal, patchy or diffuse loss of hair
17	2	Mucosal ulcers	Oral or nasal ulcerations
18	2	Pleurisy	Pleuritic chest pain or pleural rub or effusion, or pleural thickening (does not require an objective component if medically convincing)
19	2	Pericarditis	Classic pericardial pain and/or rub, effusion or ECG or echocardiogram confirmation (does not require an objective component if medically convincing)
20	2	Low complement	Decrease in CH50, C3 or C4 below lower limit of normal for testing laboratory
21	2	Increased DNA	Increased DNA binding above normal range for testing laboratory

		binding	
22	1	Fever	> 38°C. Exclude infectious cause
23	1	Thrombocytopenia	< 100 x 10  platelets/L, exclude drug causes
24	1	Leukopenia	< 3 x 10  WBC/L, exclude drug causes

**SCORE:**

### **SELENA SLEDAI FLARE INDEX** (Can be used with any version of the SLEDAI)

Note as an experimental endpoint the revised SELENA SLEDAI FLARE INDEX will also be tested

Physician's Global Assessment (PGA)  
Visual Analog Scale with anchors

0      1      2      3      (this is a three inch or 10 cm scale)  
None    Mild    Moderate    Severe

#### **Mild or Moderate Flare**

- Change in SELENA-SLEDAI instrument score of 3 points or more (but not to more than 12)
- New/worse: Discoid, photosensitive, profundus, bullous lupus,  
Nasopharyngeal ulcers  
Pleuritis  
Pericarditis  
Arthritis  
Fever (SLE)
- Increase in prednisone, but not to >0.5 mg/kg/day
- Added NSAID or hydroxychloroquine for SLE activity
- ≥1.0 increase in PGA score, but not to more than 2.5

#### **Severe Flare**

- Change in SELENA-SLEDAI instrument score to greater than 12
- New/worse: CNS-SLE  
cutaneous vasculitis,  
Vasculitis  
Nephritis  
Myositis  
Plt <60,000  
Hemolytic anemia: Hb <70 g/L or decrease in Hb >30 g/L

**Requiring:** double prednisone, or prednisone increase to  
>0.5 mg/kg/day, or hospitalization

- Increase in prednisone to >0.5 mg/kg/day
- New cyclophosphamide, azathioprine, methotrexate for SLE activity
- Hospitalization for SLE activity
- Increase in Physician's Global Assessment score to >2.5

## **GUIDELINES FOR USE OF HYBRID SLEDAI MODIFIED FOR ASSESSMENT OVER 28 DAYS: TO ASSESS DISEASE ACTIVITY**

### **General guidelines for filling out the HYBRID SLEDAI:**

**The HYBRID SLEDAI includes the definitions of proteinuria used in the SLEDAI 2K and is otherwise identical to the SELENA SLEDAI.**

- The main principle to keep in mind is that this instrument is intended to evaluate current lupus activity and not chronic damage, severity is accounted for in part by the "weightedness" of the scale.
- Points are given exactly as defined.
- A descriptor is either scored the exact points allotted or not scored, i.e. given a zero. Descriptors are scored only if they are present at the time of the physician encounter or in the preceding 28 days. Windows acceptable in a clinical trial are acceptable in scoring the SLEDAI. However, it is never acceptable to fill in gaps which cover activity over 2-3 months or more. The reason for this is that disease activity at the visit might have changed several times in such intervals and the recording of distant activity becomes meaningless.

*Please note that in the original SLEDAI the disease activity being scored was meant to cover only a ten day period, the modification to 28 days is a more useful assessment for use in clinical trials, in order to capture disease activity between monthly visits.*

- The descriptor must be documented by the notes written in the physician encounter form and generally applies to the clinical data and not to the laboratory data. The laboratory data is strictly defined as per cutoffs and documentation is provided by the reports from the commercial laboratory.
- Descriptors do not have to be new but can be. They can be ongoing, recurrent, or initial events. Each would be scored the same way. An example would be a malar rash or mucosal ulcer. In these situations a malar rash observed at the initial visit but which remains unchanged for the next six months, irrespective of any treatment, is scored 2 points each time the SLEDAI is completed. Since the nature of lupus is that manifestations are not usually fleeting it would be rare for descriptors to be present 10 days before and not at the time of the encounter. This is discussed in more detail for each descriptor but is especially relevant for the neurologic, pulmonary, and cutaneous manifestations.
- In some descriptors the exclusions written may not be exhaustive. The intent of the SLEDAI is that the descriptor be attributed to SLE. If the physician does not attribute the descriptor to SLE it should not be scored, but full documentation must be provided.

*Written in italics is the definition for each descriptor precisely provided in the SLEDAI SCORE*

### **SEIZURE**

*Definition: Recent onset (last 28 days). Exclude metabolic, infectious or drug cause, or seizure due to past irreversible CNS damage.*

This descriptor is scored if the patient has had a witnessed seizure or convincing description (such as tongue biting or incontinence) within 30 days of the current encounter. The patient need not have a positive EEG, CT scan, PET scan, QEEG, or MRI. The CSF may be totally normal.

A seizure is also not counted:

1. If a metabolic cause is determined.
2. In the presence of a proven infectious meningitis, brain abscess, or fungal foci.
3. If there is a history of recent head trauma.
4. In the presence of an offending drug.
5. In the presence of severe hyperthermia or hypothermia.
6. If the patient has stopped taking anticonvulsant medication.
7. If the patient has a documented sub-therapeutic anticonvulsant drug level.

## PSYCHOSIS

*Definition: Altered ability to function in normal activity due to severe disturbance in the perception of reality. Include hallucinations, incoherence, marked loose associations, impoverished thought content, marked illogical thinking, bizarre, disorganized, or catatonic behavior. Exclude uremia and drug causes.*

This descriptor is scored if any of the criteria above are met.

With regard to drug causes the most problematic situation is glucocorticoids. If the treating physician attributes the psychosis to glucocorticoids this descriptor should not be counted.

## ORGANIC BRAIN SYNDROME

*Definition: Altered mental function with impaired orientation, memory or other intellectual function, with rapid onset and fluctuating clinical features. Include clouding of consciousness with reduced capacity to focus, and inability to sustain attention to environment, plus at least two of the following: perceptual disturbance, incoherent speech, insomnia or daytime drowsiness, or increased or decreased psychomotor activity. Exclude metabolic, infectious or drug causes.*

- a. reduced capacity to focus as exemplified by new inability to perform everyday mathematical computations or disorientation to person, place, time, or purpose

**OR**

- b. inability to carry on a conversation

**OR**

- c. reduction in short term memory

## PLUS: Documented abnormality on neuropsychiatric testing

Neuropsychiatric testing may take the form of a "mini-mental-status exam" or a formal neuropsychiatric examination. The important aspect for scoring OBS is that it be reversible. Consideration should be given to the improvement of OBS after institution of glucocorticoids.

This descriptor is not scored in the presence of a metabolic, infectious, or drug cause. If the problem is chronic this descriptor is not scored in SLEDAI but is scored on the damage index.

## VISUAL DISTURBANCE

**Definition:** *Retinal and eye changes of SLE. Include cytoid bodies, retinal hemorrhages, serous exudate or hemorrhages in the choroid, optic neuritis, scleritis or episcleritis. Exclude hypertension, infection or drug causes.*

This is scored exactly as defined with the understanding that it must be supported by objective evidence.

## **CRANIAL NERVE DISORDER**

**Definition:** *New onset of sensory or motor neuropathy involving cranial nerves. Include vertigo due to lupus.*

This is scored exactly as defined with the understanding that it must be supported by objective evidence. However, it should be noted that hydroxychloroquine can affect the eighth cranial nerve.

## **LUPUS HEADACHE**

**Definition:** *Severe persistent headache: may be migrainous, but must be non-responsive to narcotic analgesia.*

For this descriptor to be counted, the headache must be present for greater than 24 hours and must not be responsive to narcotic analgesia. Objective documentation need not be present although it is expected that such a complaint, given the severity, would prompt formal testing such as MRI, CT, LP, etc. Furthermore, the headache should be of sufficient severity to warrant the initiation of glucocorticoids or additional immunosuppressive agents. Scoring of this descriptor means attribution of the headache to CNS lupus.

Most headaches, including most severe and/or migrainous headaches are not attributable to lupus and this descriptor should only be scored very rarely.

## **CVA**

**Definition:** *New onset of cerebrovascular accident (s). Exclude arteriosclerosis or hypertensive causes.*

This descriptor is scored if the patient has had a CVA within 28 days of the current encounter. A patient recovering from a CVA that was documented more than 28 days prior to the current encounter is not given points for this descriptor. A patient may have had a previous CVA but to be scored the current CVA must be new.

This descriptor is scored in the presence or absence of anti-phospholipid antibodies, i.e., the precise pathophysiologic mechanism need not be known.

The CVA is scored even in the presence of a normal CT or MRI. A TIA is also scored if the patient gives a convincing history. To exclude atherosclerosis the patient has to have a normal carotid and/or vertebral Doppler and cannot have uncontrolled hypertension.

## **VASCULITIS:**

**Definition:** *Ulceration, gangrene, tender finger nodules, periungual infarction, splinter hemorrhages, or biopsy or angiogram proof of vasculitis.*

To score this descriptor the above definitions must be present. For example, erythematous lesions on the hands or feet which may be characteristically considered "leukocytoclastic vasculitis" but do not fulfill at least one of the above definitions and if not biopsied, are not counted. Similarly livedo reticularis is not counted. Healed ulcers with residual scar are not to be counted, but be sure to count these in the damage index. A lesion consistent with erythema nodosum should be counted regardless of whether it is biopsied or not. Purpura in the presence of a normal platelet count should be counted regardless of whether it has been biopsied or not.

## ARTHRITIS

*Definition: More than two joints with pain and signs of inflammation, i.e., tenderness, swelling, or effusion.*

Arthritis is scored if it is ongoing; it need not be new or recurrent.

Arthritis is scored only if *more than two* joints manifest signs of inflammation. For example if only the right second and left third PIPs are involved or only both wrists, points for this descriptor are not given.

Inflammation is strictly defined in this activity index as the **presence of tenderness** (the patient complains of pain on palpating the joint or upon going through range of motion) **PLUS** any one of the following:

1. swelling
2. effusion
3. warmth
4. erythema, but must exclude overlying cellulitis

The presence of tenderness alone is not sufficient. A patient's complaints of pain in specific joints without objective findings is not sufficient. An exception would be arthritis of the hip in which case pain in the groin on range of motion accompanied by decreased range of motion in the absence of swelling, warmth, or erythema would be counted.

Inflammation of the tendons, ligaments, bursae, and other periarticular structures are not scored. For example subacromial bursitis and trochanteric bursitis are not scored. If further evaluation reveals osteonecrosis or osteoarthritis, this descriptor is not counted.

## MYOSITIS

*Definition: Proximal muscle aching/weakness, associated with elevated creatine phosphokinase/aldolase or electromyogram changes or a biopsy showing myositis.*

The patient complains of muscle aching and/or weakness in the proximal muscles **PLUS** one of the following must be present:

1. elevated serum creatine phosphokinase and/or aldolase
2. abnormalities on electromyogram consistent with myositis
3. biopsy-proven myositis

## URINARY CASTS

*Definition: Heme-granular or red blood cell casts.*

This is scored if red blood cell casts are seen, even if it is only one. Pigmented casts are counted but non-pigmented granular casts, hyaline or waxy casts are not counted.

## HEMATURIA

*Definition: >5 red blood cells/high power field. Exclude stone, infection or other cause.*

With regard to this descriptor, every attempt should be made to see patients when they are not menstruating. If this is not possible the urinalysis should be deferred until the next visit.

This descriptor is not scored if there is documented renal calculi or infection. The latter must be confirmed by a positive urinary culture. However it is acknowledged that associated conditions such as chlamydia or urethral

irritation may result in mild hematuria and the physician's best judgment is warranted. **The important point is attribution: there must be other evidence of nephritis and other causes of hematuria must be excluded.** In the complete absence of proteinuria, attribution of hematuria to active nephritis would be very unlikely unless pathology is limited to the mesangium.

## PROTEINURIA

*Definition: proteinuria of more than 0.5 g/24 hours.*

Must be attributed to active lupus nephritis.

## PYURIA

*Definition: >5 white blood cells/high power field. Exclude infection.*

This descriptor is not scored if there is evidence of vaginal contamination (presence of any squamous epithelial cells) or a documented infection. The latter must be confirmed by a positive urinary culture. However, it is acknowledged that associated conditions such as chlamydia, trichomonas or urethral irritation may result in mild pyuria and the physician's best judgment is warranted. **The important point is attribution; there must be other evidence of nephritis, and other causes of pyuria should be excluded.** In the complete absence of proteinuria, attribution of hematuria to active nephritis would be very unlikely unless pathology is limited to the interstitium.

## RASH

*Definition: Ongoing inflammatory lupus rash.*

A rash is scored if it is ongoing, new or recurrent. Even if it is identical in terms of distribution and character to that observed on the last visit and the intensity is improved, it is counted. Therefore, despite improvement in a rash, if it is still ongoing it represents disease activity. The rash must be attributable to SLE. A description of the rash must appear in the physical exam and should include distribution, characteristics such as macular or papular, and size.

The following should not be scored:

1. Chronic scarred discoid plaques in any location.
2. Transient malar flush, i.e., it is not raised and is evanescent

A common problem one may encounter is the differentiation between scoring a lesion as "rash" and/or "vasculitis". If a lesion meets the descriptive criteria of the latter it should not also be counted as rash, i.e., the score would be 8 points not 10 points. If a separate rash characteristic of SLE is present only then would "rash" also be scored.

## ALOPECIA:

*Definition: Ongoing abnormal, patchy or diffuse loss of hair due to active lupus.*

This should be scored if any of the following conditions are present:

1. There is temporal thinning which is newly present for less than six months (if temporal alopecia is present for more than six months with no change it should not be counted)

2. Areas of scalp with total bald spots if present for less than six months (does not need to have accompanying discoid lesion or follicular plugging)
3. The presence of "lupus frizz" i.e., short of strands of unruly hair in the frontal or temporal area

If a patient complains of hair loss and there is nothing apparent on exam this descriptor is not scored.

#### **MUCOSAL ULCERS:**

*Definition: Ongoing oral or nasal ulcerations due to active lupus.*

An ulcer is scored if it is ongoing, it need not be new or recurrent. Ulcers can be present in either the nose or oral cavity. Erythema alone without frank ulceration is not sufficient to be scored, even if the erythema is present on the upper palate. Ulcers on the buccal mucosa and tongue are counted.

Mucosal ulcers are not counted as vasculitis.

#### **PLEURISY**

*Definition: Classic and severe pleuritic chest pain or pleural rub or effusion or new pleural thickening due to lupus.*

This descriptor is scored if the patient complains of pleuritic chest pain lasting greater than 12 hours. The pain should be classic, i.e., exacerbated by inspiration, to help distinguish it from musculoskeletal conditions such as costochondritis, which could be confused with pleurisy. The symptom does not have to be accompanied by any objective findings. The presence of objective findings such as pleural rub or pleural effusions (in the absence of infection, congestive heart failure, malignancy, or nephrosis) is counted, even if not accompanied by symptoms. New pleural thickening should be counted only if other causes as described above are absent.

#### **PERICARDITIS:**

*Definition: Classic and severe pericardial pain or rub or effusion, or electrocardiogram confirmation.*

The symptom does not have to be accompanied by objective findings.

#### **LOW COMPLEMENT:**

*Definition: Decrease in CH50, C3 or C4 below the lower limit of normal for testing laboratory. Exclude a low C4 or CH50 in patients with known inherited deficiency of C4.*

#### **INCREASED DNA BINDING**

*Definition: >25% binding by Farr assay or above normal range for testing laboratory.*

#### **FEVER:**

*Definition: >38°C. Exclude infectious cause.*

This would be scored if one of the following conditions are present:

1. A documented temperature elevation >100.4°F or >38°C at the time of the visit.
2. A convincing history from the patient that she/he has been febrile within the preceding 10 days prior to the visit without any signs or symptoms suggestive of infection. Febrile is defined as above and not simply that the patient felt feverish. In this case the patient need not be febrile at the time of the visit for a score of 2 to be given.

As stated in the SLEDAI, fever secondary to infection is not to be scored although it is acknowledged that concomitant lupus activity and infection can occur. Fever in the presence of infection should only be scored on the SLEDAI if other evidence of lupus activity is present.

**THROMBOCYTOPENIA:**

*Definition: <100,000 platelets/mm^3.*

**LEUKOPENIA:**

*Definition: <3,000 white blood cells/mm^3. Exclude drug causes.*

This is exactly as described, WBC <3,000/mm^3. The presence of an absolute lymphopenia does not count in the SLEDAI. A note of caution, do not confuse this WBC with that used to satisfy the ACR criteria for SLE which is WBC <3,500/mm^3.

With regard to current use of possible offending drugs, the following guidelines are to be considered:

1. The nadir after cyclophosphamide, i.e., low WBC at 10 days after receiving cyclophosphamide in a patient known to have a WBC  $\geq$  3,000 at the time of receiving cyclophosphamide should not be counted.
2. Do not score leukopenia appearing after initiation of a new medication known to be associated with leukopenia, such as azathioprine or sulfa drugs. If the patient develops a WBC <3000 while taking drugs which may cause leukopenia, score this only if the dosage of medication is unchanged since the last WBC determination.

## **Revised SELENA SLEDAI FLARE INDEX**

**This instrument, shown on the next pages, can be scored (experimentally either with only the clinical components, when clinical OR treatment components are met, or with the rule that “treatment trumps.” This instrument is still under evaluation and this study will compare these different scoring options.**

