## PROTOCOL SYNOPSIS

Protocol Title:	Clarification of Abatacept Effects in SLE with Integrated Biologic and Clinical Approaches (The ABC Study) The ABC Study:
Site Numbers/ Names:	Site 1: Oklahoma Medical Research Foundation
Research Hypothesis:	Abatacept is effective in lupus arthritis and this will be discernible in a small trial with robust endpoints which incorporates withdrawal of background immune suppressants
Study Schema: Drugs / Doses / Length of Treatment)	
 
1. Abatacept or placebo will be given in a 1:1 randomization subcutaneously q week for six months. Patients may elect to continue six more months on open label Abatacept.
 
2. Background Immune Suppressants will be withdrawn at any time between screening and the first dosing visit.
 
3. At or after screening, patients may elect 40-160 mg depomedrol shots prn not to exceed 320 mg total up to and including the Month 2 Visit (two months after the first dosing visit)
 
4. Additional steroids or immune suppressants, if necessary, will be allowed but the patient will be considered a non-responder on that basis
 
5. At the 3 month visit patients with significant clinical flare unresponsive to optional per protocol treatments may elect to receive open label Abatacept but will be considered non-responders in the primary endpoint at six months.
 

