Study Objectives: 
 
• Primary:
 
• Secondary:
 
	
Primary Objective: To compare response rates between Abatacept-Treated and Placebo-Treated Patients with active lupus arthritis in a trial designed with background immune suppressant withdrawal, limited steroid rescue, and a robust, discriminatory endpoint. Statistical powering is based on this primary objective. The trial design and primary endpoint (response by BICLA) have been pre-tested by us for safety and ability to ensure placebo group non-response. This will support a rational decision about further development of abatacept for SLE at minimal cost.
 
2.) Secondary clinical endpoints will include: SRI 4/5, changes in joint counts, SLEDAI, BILAG, CLASI, PGA, and LFA simplified instrument measures. PK and immunogenicity studies will be performed to help in interpretation of outcomes. Novel biologic discovery will be integrated into the clinical trial to support both pre-specified and exploratory biomarker discovery. Data will be generated that might be used to help select more appropriate patient subsets for future trials and, along with PK data, help to guide optimal dosing strategies. Optimizing patient selection and dosing are important goals for further increasing demonstrable effect size in trials by increasing the response rates

	in the treatment group.
Study Design:	This study will be a double blind, randomized, placebo-controlled clinical trial with 1:1 randomization of patients to abatacept 125 mg weekly subcutaneous dose or placebo, with the withdrawal of background immune suppressants. Limited steroid rescue allowed per protocol. Additional meds will define non-response the primary endpoint date of six months. Flaring patients may elect to receive open label abatacept at Month 3 but will also be defined as non-responders in the primary endpoint. All patients may elect to receive open label abatacept for an additional six months after the primary endpoint date, with two follow up visits (2 and 4 months post withdrawal) to assess withdrawal effects and to complete the safety assessment.
Accrual Goal: (Total subjects)	This study will continue to recruit until we achieve the goal of 60 patients who complete study visits through the 6 month endpoint.

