### **SELENA Flare Index-Revised**

The 2009 revision of the SELENA Flare Index evaluates increases in SLE disease activity within eight organ systems: mucocutaneous, musculoskeletal, cardiopulmonary, hematological, constitutional, renal, neurological, and gastrointestinal.

Within each organ system the Investigator assesses clinical manifestations and treatment recommendations to arrive at a flare categorization as no flare, mild flare, moderate flare, or severe flare.

In the event that the assessment of a clinical manifestation and the recommendation for a treatment change are discrepant the treatment choice takes precedence (in the direction of a higher flare definition). Treatment changes recommended because of intolerance, toxicity or safety do not count towards a flare definition.

SLE manifestations within each organ system are given on the following pages.

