## 2. Musculoskeletal System

None	Mild D	Moderate D	Severe D
D	
Clinical: New/worse/recurrent polyarthralgias New/mild arthritis of 1 or 2 joints  AND/OR Treatment: any of No treatment or analgesia New/increased hydroxychloroquine or other antimalarial New/increased prednisone <math>\leq</math> 7.5 mg/day New or increased NSAID New/increased dehydroepiandrosterone (DHEA)
	
Clinical: New/worse/recurrent polyarthritidis (3 or more joints)  AND/OR Treatment: any of New/increased prednisone to <math>></math> 7.5 mg/day but <math><</math> 0.5 mg/kg/day for <math>></math> 3 days Intramuscular corticosteroid Methotrexate <math><</math> 15 mg/wk  New or increased dose of immunosuppressive (not cyclophosphamide) Intraarticular corticosteroid
	
Clinical: New/worse/ polyarthritidis (3 or more joints) with marked reduction in range of motion or mobility  AND/OR Treatment: any of New/increased prednisone <math>></math> 0.5 mg/kg/day (including IV methylprednisolone) Methotrexate <math>></math> 15 mg/wk Cyclophosphamide Rituximab or other biologic Hospitalization for severe activity

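### Two of the three scoring options for the revised flare index can grade the trial's own depomedrol and open-label abatacept as moderate or severe flares in patients with nothing new or worse

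*Combined protocol and SAP*

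**What the plan says.** Appendix 1 (Revised SELENA SLEDAI Flare Index) states that the index "can be scored (experimentally either with only the clinical components, when clinical OR treatment components are met, or with the rule that" treatment overrides the clinical finding. It then says: "This instrument is still under evaluation and this study will compare these different scoring options".

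The next section (SELENA Flare Index-Revised) gives a rule for cases where the clinical and treatment parts disagree: "the treatment choice takes precedence (in the direction of a higher flare definition". It offers one exemption: "Treatment changes recommended because of intolerance, toxicity or safety do not count towards a flare definition".

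The musculoskeletal table lists "Intramuscular corticosteroid" in the moderate column and "Rituximab or other biologic" in the severe column. The other seven organ tables carry the same two items (the constitutional table shortens the first to intramuscular steroid). Clinical and treatment items are joined by and/or.

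The protocol provides both treatments. Under item 3 of the Synopsis Study Schema, "patients may elect 40-160 mg depomedrol shots prn not to exceed 320 mg total", up to and including the Month 2 visit; Section 5.1 confirms that the route is intramuscular. The Synopsis Study Design adds: "All patients may elect to receive open label abatacept for an additional six months after the primary endpoint date". Section 4.1 also allows an open-label start at Month 3 if disease activity has not improved from baseline. Section 9.2 refers to abatacept as a biologic.

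**The concern.** The revised index is meant to detect rises in lupus activity. A patient who responds through Month 6 and then accepts the open-label offer has had no rise, yet now receives a drug that sits in the severe column. A patient who enters with active arthritis, as every patient must, and has a depomedrol shot for that same unchanged arthritis meets a moderate item. Nothing in Appendix 1 exempts treatment that the protocol itself makes available.

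At stake is the comparison that Appendix 1 announces. If protocol-supplied treatment is counted, part of the gap between the clinical-only score and the two treatment-based scores comes from the trial design and not from the instrument. There is a possible second consequence. Section 8 sends flare data to the DSMB, asks it to compare them with the earlier abatacept lupus trials, and allows unexpected flare reports to trigger unblinding. It does not say which flare index or scoring option supplies those data.

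**Working it through.** The plan gives no figure on this point, so the check sets the scoring rules against the protocol-supplied treatments.

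**Step 1. Grade each treatment on its own, with no new or worse manifestation, reading the items as written.**

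| Scoring option | Depomedrol (intramuscular steroid item) | Open-label abatacept (biologic item) |
|---|---|---|
| Clinical only | no flare | no flare |
| Clinical or treatment | moderate | severe |
| Treatment overrides | moderate | severe |

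Two of the three options give a flare. The stated precedence rule leads to the same result: the clinical part says none, the treatment part says moderate or severe, and the higher grade wins.

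**Step 2. Look for an exemption.** The only one covers changes made for tolerability or safety. Elective depomedrol and elective open-label abatacept are neither. The prednisone items are qualified as new or increased; the biologic item is not, so continuing abatacept is no more clearly excluded than starting it.

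**Step 3. Identify which uses can occur without worsening.**
- Depomedrol, screening to Month 2: given as needed. Some shots will accompany real worsening; others may treat arthritis that is unchanged since entry.
- Open label at Month 3: the entry condition differs by place. Synopsis item 5 requires a significant clinical flare, Section 4.1 requires only lack of improvement, and Section 5.3 allows either. Under the Section 4.1 wording no worsening is needed. These passages must be reconciled.
- Open label after Month 6: offered to all patients, with no flare condition.

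**Step 4. Bound the number of patients.** The documents give no uptake. For the Month 6 offer, with 60 patients completing Month 6 (the accrual goal) and an assumed uptake u, the ceiling is u × 60:
- u = 0%: 0
- u = 50%: 0.50 × 60 = 30
- u = 100%: 1.00 × 60 = 60

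These are ceilings on gradings that the rules permit, not forecasts. With about 30 completers expected per arm, roughly half of those electing would be continuing abatacept and not newly starting it. For depomedrol the affected number likewise lies between none and all who elect a shot.

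**Step 5. Check what else could be affected.** The original SELENA SLEDAI Flare Index in Appendix 1 lists neither intramuscular steroid nor biologics. BICLA (Section 6.4.1) does not use the revised index. Appendix 1 calls the revised index experimental, it is not in the secondary or exploratory clinical lists, and Section 9 contains no analysis of it.

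**The case against.** The strongest reply is that a treatment item cannot have been meant to score a flare by itself. The mild columns include receiving no treatment, joined by the same and/or; read literally, every quiet, untreated patient would have a mild flare in every organ system at every visit. Patients on blinded abatacept would also meet the biologic item from their first dose. The items make sense only as a response to worsening in that organ, and a patient accepting an offer made to everyone is not an investigator recommending treatment for such worsening. An investigator could reasonably decline to score it.

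This stands as a limit on certainty. A reader might infer that every depomedrol shot and every open-label start will be recorded as a flare. The documents do not support that: the clinical-only option ignores both treatments, some uses will accompany genuine flares, screening and baseline shots come before on-treatment follow-up, and investigator judgement is left open.

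It does not remove the problem. The precedence rule is written for exactly the case where the clinical and treatment parts disagree, and it resolves that case upward. A shot for unchanged arthritis, or a Month 3 start for disease that has merely not improved, falls within it. Leaving the Month 6 offer to judgement means two investigators could score the same patient differently.

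It is also fair to say that showing how far treatment items move the score is the purpose of the comparison. That purpose is served only if treatment follows disease activity. For the Month 6 offer it need not.

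A reader might further infer that DSMB flare counts are inflated. No section links the revised index to the DSMB, and the Section 6.1 schedule names only SLEDAI/SSFI/PGA. That consequence remains conditional.

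**Conclusion.** The point holds in a limited form. Under the two options that count treatment, and under the stated precedence rule, depomedrol (to Month 2) and elective open-label abatacept (at Month 3 for disease not improved, and for all patients after Month 6) can be graded moderate or severe flares with no new or worse manifestation, because the sole exemption does not reach them.

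The effect is confined to an experimental endpoint. The number of patients lies between none and all who elect, and a point estimate of artefactual flares would need an uptake that the documents do not give. The conclusion assumes that investigators follow the precedence rule as written; if they score treatment only when it answers a worsening in that organ, the effect shrinks, but the text does not tell them to do so. The primary result, the sample size and the original flare index do not depend on this. It is worth correcting because it would distort the comparison of scoring options, and no later analysis section would resolve it.

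**What to change.** In Appendix 1 (SELENA Flare Index-Revised), extend the exemption so that starting or continuing open-label abatacept under the general Month 6 offer is not a treatment criterion.

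Do not exempt all protocol treatment. Some depomedrol use and some Month 3 open-label starts will accompany a real flare, and removing them would blunt the comparison. For these, keep the treatment-based scores, flag each use that has no recorded new or worse manifestation, and report the comparison of options with and without the flagged uses.

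Reconcile the two adjoining Appendix 1 sections: one presents treatment precedence as the rule of the instrument, the other as one of three options. Reconcile the Month 3 open-label condition across the Synopsis, Section 4.1 and Section 5.3, since the scoring flag depends on it; which condition is right is for the sponsor and investigator.

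In Section 8, state that flare data sent to the DSMB use the original index or the clinical-only score.

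The cost is a short paragraph in Appendix 1, a sentence in Section 8, one extra flag on the flare form and one extra tabulation. The scoring changes alter no treatment rule.
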